3.4.2. Secondary Efficacy Endpoints

CA-125 Response Rate:

The CA-125 response rate is defined as the proportion of patients having a CA-125 response according to the GCIG criteria:

- A response according to CA-125 is observed when there is at least a 50% reduction in CA-125 level from baseline. The response must be confirmed and maintained for at least 28 days.
- Patients can be evaluated according to CA-125 if they have a pre-treatment sample that is at least twice the upper limit of normal (ULN) and within 2 weeks prior to starting treatment

3.5. Safety Analyses

Safety analyses will be performed on the **Safety Population**.

3.5.1. Extent of Exposure

Number of Cycles, Duration of Treatment, Cumulative Dose and Relative Dose Intensity (RDI) will be summarized by treatment for the safety population.

CC-486:

Number of Cycles: number of cycles having total dose > 0 mg reported

Duration of Exposure (day) = sum of [(Date of last dose - Date of first dose + 1) of cycle]

Duration of Treatment (day) of each administration sequence = (Date of last dose – Date of first dose + 1)

Cumulative Dose (mg) = sum of (Duration of Treatment of each administration sequence × daily dose)

Dose Intensity (mg/day) = (Cumulative Dose) ÷ (Duration of Exposure)

Planned Dose Intensity (mg/day) = Planned Daily Dose as per cohort
RDI (%) = (Dose Intensity ÷ Planned Dose Intensity) × 100

The compliance of CC-486 will be summarized by cycle using the following calculation:

$$\text{Compliance (\%)} = \frac{\text{Number of Tabs taken} + \text{Number of Tabs Returned}}{\text{Number of Tabs Dispensed}} \times 100$$

Pembrolizumab:

Number of Cycles: number of cycles having total dose > 0 mg reported
Duration of Treatment (weeks) = [(Date of last dose - date of first dose) + 21] ÷ 7
Cumulative Dose (mg) = sum of total dose administered as reported
Weekly Dose Intensity (mg/week) = (Cumulative Dose) ÷ (Duration of Treatment)
Planned Weekly Dose Intensity (mg/week) = 200mg ÷ 3 weeks
RDI (%) = (Weekly Dose Intensity ÷ Planned Weekly Dose Intensity) × 100

The RDI will be additionally presented categorized (i.e., number and percentage of patients with RDI of < 60%, 60 - < 80%, 80 - < 90%, 90 - < 110%, ≥ 110%).

The number and percentage of patients with dose modifications will be summarized. The respective reasons of dose modification will be listed.

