5.7.3.2 Treatment Schedule Adjustments and Management of CC-486 Toxicities

During CC-486 treatment subjects should receive appropriate supportive care measures as deemed necessary by the Investigator considering the recommendations provided in this section.

Table 4: CC-486 dose modifications for hematologic toxicity

Toxicity	Recommendation

Grade 2-3 neutropenia on any testing*
 
* If grade ≥ 3 associated with fever at any time, the dose adjustment guidelines for grade 4 neutropenia should be enacted.
	
For Schedule 1, withhold CC-486 until recovery to \leq Grade 1. After recovery, resume CC-486 at the same dose. If no recovery from neutropenia to \leq Grade 1 is observed after 14 days of neutropenia diagnosis, permanently discontinue CC-486.
 
For Schedules 2, 3 and 4, temporarily reduce CC-486 one dose level as per Table 3 until cycle completion. If no further reduction is allowed as per Table 3, temporarily withhold CC-486 until next cycle.
 
At next CC-486 cycle:
 
 • If recovery to \leq Grade 1, re-escalate CC-486 to the previous dose (i.e. dose administered prior to the temporary reduction/interruption). • If no recovery from neutropenia to \leq Grade 1 is observed after 14 days of neutropenia diagnosis, permanently discontinue CC-486. 
Note: In cases of recurrent neutropenia (grade 3/4) after two temporary dose reductions/interruptions, CC-486 will be permanently discontinued.

Toxicity	Recommendation

Grade 4 neutropenia on a pre CC-486 hematology testing or during CC-486 treatment
	
All schedules: Withhold CC-486 until next cycle and monitor ANC until recovery to \leq Grade 1.
 
 • If recovery \leq 7 days: at next cycle, resume CC-486 at the same dose (i.e. dose administered prior to the interruption). • If no recovery $>$ 7 days: permanently discontinue CC-486 
Initiation of G-CSF should be considered by the Investigator. If initiated, administer G-CSF per institutional practice or package insert and continue until ANC recovers to $\geq 2.0 \times 10^9/L$.
 
Note: In cases of recurrent neutropenia (grade 3/4) after two temporary dose reductions/interruptions, CC-486 will be permanently discontinued. In cases where as a consequence of previous toxicity no additional dose reductions are allowed as per Table 3, CC-486 could be temporarily interrupted until next cycle.

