3.2.3. Date of Last Dose

The date of last dose (of study drug) is derived as the last date when a non-zero and non-missing dose of study drug is administered.

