5.1. Planned Tables

Title	Population	Description
Patient Disposition	ITT	Tabulates the disposition of all patients by cohort, including the number of patients in each population set, discontinued from study treatment, and discontinued from study. The reason for drug discontinuation and study discontinuation will also be summarized.
Protocol Deviations	ITT	Tabulate the number of patients who reported protocol deviations by deviation category for each cohort.
Eligibility Deviations	ITT	Tabulates the number of patients who violates inclusion/exclusion criteria by criterion for each cohort
Patient Demographics	ITT Safety	Tabulates summary statistics of patient demographics (age, race, ethnicity, weight and ECOG status at baseline) for each cohort.
Disease Characteristics	ITT	Tabulates summary statistics for time from initial diagnosis to enrollment, primary tumor location, staging at initial diagnosis, histopathological type at initial diagnosis, histopathological grade at initial diagnosis, disease status at enrollment, time from first progression/relapse to enrollment for each cohort.
Prior Surgery for Ovarian Cancer	ITT	Tabulates the number of patients with type of procedures for each cohort.
Prior Systemic Anti-Cancer Therapy	ITT	Tabulates the number of regimens received by patient according to type and indication of the systemic cancer therapy for each cohort.
Medical History	ITT	Summarizes medical history by SOC and PT for each cohort.
Study Drug Exposure	Safety	Summarizes the number of cycles, the duration of treatment, cumulative dose, and RDI by cohort. The number of dose modification will also be summarized by study drug.

Title	Population	Description
Compliance	Safety	CC-486 Compliance assessment will be summarized by each cycle.
Best Overall Response/irORR and irDCR	ITT	Summary of Best Overall Response as per irRECIST will be tabulated by cohort irORR and irDCR will also be reported
CA-125	ITT	Summary of CA-125 Response Rate will be tabulated by cohort.
AEs Overview	Safety	Tabulates the number of patients with AEs, Related AEs, Grade 3 / 4 AEs, AEs with action taken dose reduced, AEs with action taken drug interrupted, AEs leading to drug withdrawn, SAEs, Fatal AEs.
AEs	Safety	Summary by SOC and PT of number of patients and events for each cohort.
Related AEs – CC-486	Safety	Summary by SOC and PT of number of patients and events for each cohort.

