5.2. Planned Listings

Title	Population	Description
Patient Accountability	ITT	Listing of all patients and with population indicators. For patients who discontinued from treatment and/or study, include the reason of respective discontinuations.
Deaths	ITT	Listing of patients who died, including primary cause of death, date of death, date of last dose, and the number of days from date of last dose to death.
Patient Demographics	ITT	Listing of patient demographics.
Disease Characteristics	ITT	Listing of disease characteristics.
Prior Surgery for Ovarian Cancer	ITT	Listing of prior surgery for ovarian cancer.
Prior Systemic Anti-Cancer Therapy	ITT	Listing of prior systemic anti-cancer therapy.
Study Drug Exposure	Safety	Listing of patients for extent of exposure by cycle.

Title	Population	Description
Study Drug Exposure Summary	Safety	Listing of patients for summary of exposure (e.g. number of cycles, duration of treatment, cumulative dose, dose intensity, RDI).
Efficacy Parameters	ITT	Listing of best overall response for each patient
Tumor Assessment	ITT	Listing of tumor assessment including lesion number, date of assessment, lesion measurement/response, and time-point overall response.
CA-125	ITT	Listing of CA-125 reported for each patient.
AEs	Safety	Listing of all AEs for each patient; the listing includes the verbatim term, PT, SOC, seriousness, worst grade, start date, outcome, stop date, relationship to study drug, and action taken for study drug.
Related AE – CC-486	Safety	Listing of AEs in this category using the same structure as the AEs listing.
Related AE – Pembrolizumab	Safety	Listing of AEs in this category using the same structure as the AEs listing.
SAEs	Safety	Listing of AEs in this category using the same structure as the AEs listing.
Grade 3 / 4 AE	Safety	Listing of AEs in this category using the same structure as the AEs listing.
AEs Leading to Death	Safety	Listing of AEs in this category using the same structure as the AEs listing.
AEs with Action Taken for Dose Reduced – CC-486	Safety	Listing of AEs in this category using the same structure as the AEs listing.
AEs with Action Taken for Drug Interrupted – CC-486	Safety	Listing of AEs in this category using the same structure as the AEs listing.
AEs with Action Taken for Drug Interrupted – Pembrolizumab	Safety	Listing of AEs in this category using the same structure as the AEs listing.

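### The SAP's CC-486 relative dose intensity stays at 100% when a cycle is cut short at full dose or starts late, so it overstates delivered dose and can rank a worse course above a milder one

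*SAP*

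**What the plan says.** For CC-486, SAP 3.5.1 takes dose intensity as cumulative dose divided by duration of exposure. It defines "Duration of Exposure (day) = sum of [(Date of last dose - Date of first dose + 1) of cycle", and the comparator as "Planned Dose Intensity (mg/day) = Planned Daily Dose as per cohort". RDI is the ratio of the two, times 100. SAP 3.2.3 says the date of last dose "is derived as the last date when a non-zero and non-missing dose of study drug is administered". Planned days on treatment and the 28-day cycle length appear nowhere in the calculation.

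For pembrolizumab the same section uses elapsed time: "Duration of Treatment (weeks) = [(Date of last dose - date of first dose) + 21", converted to weeks, against 200 mg per 3 weeks.

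RDI is also put into five bands: below 60%, 60 to below 80%, 80 to below 90%, 90 to below 110%, and 110% or more. The exposure table in SAP 5.1 "Summarizes the number of cycles, the duration of treatment, cumulative dose, and RDI by cohort". SAP 5.2 adds a "Listing of patients for extent of exposure by cycle".

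Protocol Table 4 (section 5.7.3.2) directs, for grade 4 neutropenia in all schedules: "Withhold CC-486 until next cycle and monitor ANC until recovery". For grade 2-3 neutropenia in Schedules 2 to 4 it directs: "temporarily reduce CC-486 one dose level as per Table 3 until cycle completion". Protocol 5.3.3 fixes the on-treatment period at 21 days (14 in Schedule 3), so missed days are not made up. Protocol 5.7.1 allows toxicity holds of up to 14 days, not counting the off-period.

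**The concern.** An RDI set against the planned regimen should fall when planned dose is not given or is given late. This one falls for dose reductions and for gaps followed by resumption in the same cycle. It does not fall when dosing stops for the rest of a cycle or when the next cycle is postponed. Protocol Table 4 directs both courses for haematologic toxicity, so they are not rare protocol departures.

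Three consequences follow:

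- Patients can be ordered wrongly, and placed in the wrong RDI band.
- The bias can differ between cohorts. Protocol 5.7.3.1 allows no dose reduction in Schedule 1, so loss there comes as withheld days, which RDI misses unless dosing resumes in the same cycle. Schedules 2 to 4 lose dose partly through reductions, which RDI registers.
- The RDIs for CC-486 and pembrolizumab, reported in the same bands, measure different things.

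**Working it through.** **Planned dose.** The SAP gives no numeric RDI to reproduce, but the planned cycle dose can be checked. Daily dose times days on (Protocol 5.3.3) is 100 × 21, 200 × 21, 300 × 14 and 300 × 21, or 2,100 / 4,200 / 4,200 / 6,300 mg for Schedules 1 to 4. This matches the 21 / 42 / 42 / 63 tablets of 100 mg in Protocol 5.1. Over 4 weeks it is 525 / 1,050 / 1,050 / 1,575 mg per week.

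**General result.** Suppose a patient takes full daily dose D on consecutive days in every cycle and stops after d₁, d₂, … days. Cumulative dose is D × (d₁ + d₂ + …) and duration of exposure is d₁ + d₂ + …. Dose intensity is then D, and RDI is D ÷ D = 100%, whatever the stopping days and whatever the interval between cycles.

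**What the formula does capture.** Schedule 4, one cycle, dosing on days 1-7 and 15-21: 4,200 ÷ 21 ÷ 300 = 66.7%, the same as 4,200 ÷ 6,300 of planned dose.

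**What it misses.** Each case has two cycles. Day 8 and day 15 are assumed onset days, chosen because Protocol 6.3.2.1 schedules haematology then. Cycle 2 is given in full.

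| Course | Cumulative dose (mg) | SAP RDI | Correct figure |
|---|---|---|---|
| Sch. 4, grade 4 neutropenia, withheld from day 8 of cycle 1 | 7×300 + 21×300 = 8,400 | 8,400 ÷ 28 ÷ 300 = 100% | 8,400 ÷ 12,600 = 66.7% |
| Sch. 4, grade 2-3 neutropenia, 200 mg from day 8 of cycle 1, then re-escalated | 7×300 + 14×200 + 21×300 = 11,200 | 11,200 ÷ 42 ÷ 300 = 88.9% | 11,200 ÷ 12,600 = 88.9% |
| Sch. 1, grade 2-3 neutropenia, withheld from day 15 of cycle 1, not recovered by day 21 | 14×100 + 21×100 = 3,500 | 3,500 ÷ 35 ÷ 100 = 100% | 3,500 ÷ 4,200 = 83.3% |
| Sch. 2, grade 2-3 neutropenia, 100 mg q.d. from day 15 of cycle 1 | 14×200 + 7×100 + 21×200 = 7,700 | 7,700 ÷ 42 ÷ 200 = 91.7% | 7,700 ÷ 8,400 = 91.7% |
| Sch. 1, grade 2 thrombocytopenia, cycle 2 delayed 14 days, same dose | 4,200 | 4,200 ÷ 42 ÷ 100 = 100% | (4,200 ÷ 10 weeks) ÷ 525 = 80% |
| Same, delayed 7 days | 4,200 | 100% | (4,200 ÷ 9 weeks) ÷ 525 = 88.9% |

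In the first pair the worse course lands in the 90 to below 110% band and the milder one in the 80 to below 90% band. In the second pair a Schedule 1 patient who received 83.3% scores above a Schedule 2 patient who received 91.7%.

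**Compliance does not fill the gap.** SAP 3.5.1 computes it as tablets taken plus returned, over tablets dispensed. It also stays near 100% when a cycle is cut short and the unused tablets come back.

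**The case against.** The strongest reply is that the formula is internally consistent: it measures average daily dose over the days of dosing, and Protocol 8.3 asks for RDI without defining it. That is true, but a figure called relative dose intensity and banded as a percentage of plan will be read as delivered against planned dose, and the pembrolizumab version in the same section behaves that way.

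The SAP says it follows protocol version 2.0, and the document history shows that version 3.0 changed the neutropenia rules in Table 4. The neutropenia examples therefore describe patients managed under the current text. The formula's behaviour does not depend on the version.

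Other outputs would expose the loss: cumulative dose, dose modifications, AEs with CC-486 interrupted or withdrawn, grade 3/4 AEs, laboratory shift tables and by-cycle listings. With about five evaluable patients per cohort these can be read directly, and RDI is not among the selection criteria in Protocol 3.3. This stands, and it limits the consequence.

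The cohort effect is a possibility only; the documents do not allow its size or direction to be estimated.

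Calendar time also charges delays unrelated to toxicity, which Protocol 5.7.1 allows up to 21 days: two full cycles would then score 56 ÷ 77 = 72.7%. That is how the pembrolizumab RDI already treats a delay between infusions, and it suits a measure of dose delivered on schedule, but the SAP should say so. The pembrolizumab formula has its own limit: it ends 21 days after the last infusion, so it misses a hold that ends in discontinuation.

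**Conclusion.** The concern holds. Truncation at full dose and late cycle starts both give exactly 100%. The bias is upward only, because the fixed on-period keeps the observed span from exceeding the planned days. In the worked two-cycle cases the overstatement runs from 11.1 to 33.3 percentage points, and patients can be ranked in the wrong order.

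The sizes depend on the assumed onset days and on cycle 2 being given in full; the 100% result does not. It does assume that the non-zero last-dose rule of SAP 3.2.3 also applies within each cycle. No endpoint and no stated selection rule changes, so this should be corrected as a supporting tolerability measure.

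**What to change.** Replace the CC-486 formula in SAP 3.5.1 with:

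RDI (%) = (cumulative dose ÷ actual calendar weeks) ÷ (planned dose ÷ planned weeks) × 100.

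- Actual time runs from first dose to the planned end of the last cycle started, delays included.
- Planned dose is 2,100 / 4,200 / 4,200 / 6,300 mg per 28-day cycle for Schedules 1 to 4.
- If progression, death or data cutoff ends the last cycle early, count planned dose and time only up to that date. For Schedule 4 with progression on day 14 of cycle 2 and every dose taken, planned dose to date is 6,300 + 14 × 300 = 10,500 mg, so RDI is 100%. Charging the whole cycle would give 10,500 ÷ 12,600 = 83.3%; a flat weekly rate would give (10,500 ÷ 6) ÷ 1,575 = 111%.
- State that delays of any cause count, and that a last cycle ended for another reason, such as toxicity of either drug or consent withdrawal, is charged to its planned end.

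The cost is one formula and one last-cycle rule, using doses, dates and discontinuation reasons already collected. Reported RDI will look less favourable, and programming takes slightly longer.

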5.1 CC-486

All subjects in Part A and subjects randomized to Arm A of Part B will receive oral CC-486 at the dosing described in sections 5.3.3 and 5.3.4.

At each visit during the treatment phase, subjects should be given container(s) with enough 100 mg tablets for one full CC-486 treatment cycle (defined as 21 or 14 days on-treatment followed by 7 or 14 days off-treatment (depending on the cohort)) of the corresponding schedule/arm (refer to section 5.3).

In Part A, the following number of 100 mg tablets would be needed for a subject to complete one CC-486 cycle of treatment, assuming no dose delays or interruptions or dose reductions from the starting dose level:

- Schedule 1: 21 tablets of 100 mg
- Schedule 2: 42 tablets of 100 mg
- Schedule 3: 42 tablets of 100 mg
- Schedule 4: 63 tablets of 100 mg

The number of tablets may need to be adjusted in case of dose modifications.

For the purpose of this trial, the Single Reference Document to be used for CC-486 is the azacitidine IB.

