5.3.5 Treatment Compliance

The administration of all study treatments should be recorded in the appropriate sections of the eCRF.

Additionally, for CC-486, treatment compliance will be assessed at each visit during treatment phase. Subjects will complete a diary to document their daily intake. They will be instructed to return all unused drugs (partially used and empty containers) and their diary at each visit. Site staff will perform accountability of the returned drug and will assess compliance of the subject. Site staff must ensure that the subject clearly understands the directions for self-medication and follows the schedule adequately.

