5.4.3 Accountability, Drug Return/Destruction

The Investigator is responsible for keeping accurate records of the clinical supplies received from the sponsor or designee, the amount administered or dispensed to and returned by the subjects, and the amount remaining at the conclusion of the trial.

TRIO will provide appropriate documents (e.g. drug inventory log or similar) that must be completed for drug accountability and return.

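### The SAP's CC-486 compliance formula adds returned tablets to tablets taken, so it measures drug accountability and reads 100% for any intake when the counts reconcile

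*SAP*

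**What the plan says.** SAP section 3.5.1 (Extent of Exposure) introduces the measure with "The compliance of CC-486 will be summarized by cycle using the following calculation". The numerator is the number of tablets taken plus "Number of Tabs Returned"; the denominator is the number dispensed; the ratio is multiplied by 100. The SAP does not say where the count of tablets taken comes from. The planned output is in SAP section 5.1, for the Safety Population: "CC-486 Compliance assessment will be summarized by each cycle".

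Protocol section 5.3.5 sets out what is collected: "Subjects will complete a diary to document their daily intake". Unused drug and the diary come back at each visit, and "Site staff will perform accountability of the returned drug and will assess compliance of the subject". Protocol section 5.4.3, on accountability, requires records of "the amount administered or dispensed to and returned by the subjects".

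The tablets needed for a full cycle are in protocol section 5.1, starting with "Schedule 1: 21 tablets of 100 mg", then 42, 42 and 63 for Schedules 2, 3 and 4.

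**The concern.** A compliance measure should fall when a subject takes less than was prescribed. Here each untaken tablet that is returned goes into the numerator and cancels the miss. Leftover tablets are also expected: under protocol section 5.3.3.1 a dose more than 6 hours late is skipped and not made up, and after vomiting no further drug is taken that day.

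CC-486 is self-administered for 14 or 21 days per cycle. The results of the SAP analyses go to the Steering Committee (SAP section 4), which compares four cohorts of at least five evaluable subjects each. A compliance table close to 100% throughout could be taken as evidence that each cohort received its assigned schedule, when the table cannot show that.

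**Working it through.** **Inputs.** Tablets per cycle come from protocol section 5.1. The compliance, cumulative dose and relative dose intensity (RDI) formulas come from SAP section 3.5.1. Return of unused drug comes from protocol section 5.3.5.

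**1. Reproduce the planned tablet counts** (100 mg tablets per day × days on treatment):
- Schedule 1: 1 × 21 = 21
- Schedule 2: 2 × 21 = 42
- Schedule 3: 3 × 14 = 42
- Schedule 4: 3 × 21 = 63

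All four match the protocol. The SAP states no compliance value or threshold to reproduce.

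**2. The ratio when counts reconcile.** If every tablet is either taken or returned, taken + returned = dispensed, so the SAP ratio is 100% by identity. If tablets taken were derived as dispensed minus returned, this would hold always, even with lost tablets.

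| Case | Taken | Returned | SAP compliance | Taken / planned |
|---|---|---|---|---|
| Schedule 1 | 14 | 7 | (14+7)/21 = 100% | 14/21 = 66.7% |
| Schedule 1 | 7 | 14 | (7+14)/21 = 100% | 7/21 = 33.3% |
| Schedule 2, one of two daily doses missed throughout | 21 | 21 | (21+21)/42 = 100% | 21/42 = 50% |
| Schedule 4 | 42 | 21 | (42+21)/63 = 100% | 42/63 = 66.7% |
| Schedule 4 | 0 | 63 | (0+63)/63 = 100% | 0/63 = 0% |

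**3. When the ratio does move.**
- Lost tablets. Schedule 2 with 28 taken, 7 returned and 7 lost: (28+7)/42 = 83.3%, against intake of 28/42 = 66.7%. A missed tablet that is not returned lowers the ratio, but cannot be told apart from any other lost tablet.
- Diary and count disagree. Schedule 1 with 7 returned: a diary count of 21 gives (21+7)/21 = 133.3%; a diary count of 10 gives (10+7)/21 = 81.0%. The tablet count implies (21−7)/21 = 66.7% in both.

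**4. Do the exposure outputs fill the gap?** The SAP builds dose from date spans: "Cumulative Dose (mg) = sum of (Duration of Treatment of each administration sequence" multiplied by the daily dose. Dose intensity is that total divided by the first-to-last-dose span of each cycle, and RDI divides it by the planned daily dose. On Schedule 1:
- Days 1–7 taken, then stopped: cumulative dose 7 × 100 = 700 mg of a planned 2,100 mg; exposure 7 days; RDI = (700/7)/100 = 100%. Cumulative dose shows the early stop; RDI does not.
- Alternate days 1, 3, …, 21 (11 tablets, 11/21 = 52.4%). Entered as one sequence: 21 × 100 = 2,100 mg over 21 days, RDI 100%. Entered as 11 sequences: 1,100/21 = 52.4 mg/day, RDI 52.4%. SAP compliance is (11+10)/21 = 100% either way.

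The eCRF is not in the documents, so which of the last two applies is unknown.

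**5. Choice of denominator for a corrected measure.** Suppose a Schedule 4 subject is reduced to 200 mg from day 8 and takes every prescribed tablet: 7 × 3 + 14 × 2 = 49. Against dispensed tablets this is 49/63 = 77.8%; against prescribed tablets it is 49/49 = 100%. The denominator has to be tablets prescribed.

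**The case against.** The strongest reply is that little depends on the table. It is descriptive, Part A has no formal sample size, compliance is not among the selection criteria in protocol section 3.3, and the site's own compliance assessment under protocol section 5.3.5 does not use this formula. That is right, and it limits the importance of the point.

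A second reply is that the ratio may have been intended as a reconciliation of diary against tablet count, which is a useful check, and that protocol section 5.3.5 can be read as accountability feeding the compliance assessment. If so, only the label is wrong. But the SAP would then contain no adherence measure, so a correction is needed on either reading.

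Third, other outputs show part of what the table misses: cumulative dose, the by-cycle exposure listing, dose modifications with their reasons, and the tables and listings of adverse events leading to interruption or reduction of CC-486. With a minimum of about 20 subjects the listings can be read directly. These outputs cover early stopping and interruptions due to toxicity. They do not reliably show forgotten doses. The RDI part of the argument does rest on an unseen eCRF, which is why it is given as a range.

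Finally, the table would not read exactly 100% for everyone, because losses and diary errors move it. That is correct; the 100% result is conditional on the counts reconciling.

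**Conclusion.** The point holds. As written, the formula cannot distinguish a tablet missed and returned from one taken. With reconciled counts it gives 100% for any true intake from 0% to 100%; otherwise it reflects lost tablets or record disagreement. This follows from the formula alone and needs no assumption beyond reconciliation, which is what the return instruction aims for.

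The consequence is one misleading descriptive table in the Part A Safety Population, with no effect on a test, sample size or analysis population. It should be fixed because the stated rule, followed exactly, gives an uninformative result under a label that readers will take at face value. How far RDI compensates is uncertain, since that depends on how dosing gaps are recorded.

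**What to change.** Replace the formula in SAP section 3.5.1 with: compliance (%) = tablets taken according to the diary ÷ tablets prescribed for that cycle at the dose level in force, excluding protocol-directed holds, × 100. Name the diary as the source of tablets taken. State how omissions the protocol itself directs, such as no further drug on a day with vomiting, are counted; this matters most for the twice-daily schedule.

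Report dispensed minus returned only as a labelled cross-check, because it counts lost tablets as taken. The present ratio can stay if relabelled drug accountability (%).

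The cost is a revised definition in the SAP, a table label, and some programming to derive prescribed tablets per cycle when the dose is reduced or held mid-cycle. The diary and returned-tablet counts are already collected under protocol section 5.3.5, and prescribed tablets follow from protocol section 5.1 and the dosing records. That the diary count is entered in the eCRF is an assumption to confirm; tablets taken is already a term in the SAP formula.
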